#### 8.0 STATISTICAL CONSIDERATIONS

#### 8.1 Sample size estimation

The primary goal of this study is to determine the efficacy and safety profile of treatment with *Serenoa Repens* compared to placebo. The primary end point of the study is change in AUA symptom score from baseline to 72 weeks. The sample size estimate is based on the following assumptions: a difference in the change in the AUA symptom score from baseline to 72 weeks of 2 points between the placebo arm and the phytotherapy arm, a common standard deviation of the AUA symptom score of 6 points, a two-group t- test, a one-sided significance level of 0.05 and a statistical power of 90%. A one-sided statistical test will be used since an improvement in the AUA symptom score with therapy (i.e., efficacy of therapy) is of primary interest. To detect the hypothesized difference in the change in the AUA symptom score, a sample size of 157 participants per arm will be required. Therefore, a total of 314 participants will be required for the study. To allow for a 10% dropout rate over the course of the study, 350 participants will be recruited to the study.

To determine the power for evaluating safety by measuring hematology and serum chemistry levels, it is assumed that the underlying probability of a severe or life-threatening adverse event detected by laboratory results for placebo is < 2.5%. With 157 participants in each treatment arm, the power to detect a severe or life-threatening adverse event that occurs with frequency  $\ge 10\%$  in the phytotherapy arm at the one-sided 0.05 significance level is 80%.

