Complete blood counts and serum chemistry measurements will be categorized by severity grade from the NCI Common Toxicity Criteria. For each participant and each time period on a dose level (1-24 weeks = level 1, 25-48 weeks = level 2, 49-72 weeks = level 3), the most severe grade of a laboratory level will be taken. For each dose level and laboratory measure, the proportions of participants who have abnormalities of severity grade 3 or greater will be compared between the phytotherapy and placebo arms using Fisher's exact test. A two-sided 0.05 significance level will be used for these comparisons.

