#### 8.2.4 Safety Analysis

Adverse event data will be summarized by treatment arm to capture the proportion of participants reporting at least one episode of a specific adverse event (incidence table), incidence of adverse events causing withdrawal, and incidence of serious adverse events. The total number of episodes for each event reported (frequency table), and the severity and attribution to treatment arm of each episode reported within body system (severity and attribution table), will also be displayed by treatment arm. Listings of adverse events by participants and event will also be provided. Comparisons of incidence of each adverse event between treatment and placebo will be performed using the two-group chi-square test, or Fisher's exact test when the assumptions for the chi-square test are not tenable. A two-sided statistical test with a significance level of 0.05 will be used for these analyses. In addition, 95% confidence intervals will be computed for differences in proportions of adverse events between study arms.

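### The 80% laboratory-safety power in section 8.1 is for a one-sided test, but section 8.2.3 plans two-sided Fisher's exact tests, with about 74% power at the stated rates and 157 per arm

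*Combined protocol and SAP*

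**What the plan says.** Section 8.1 (Sample size estimation) first derives 157 per arm from the AUA symptom score, then gives a separate power statement for safety assessed through hematology and serum chemistry. It assumes that the probability of a severe or life-threatening "adverse event detected by laboratory results for placebo is < 2.5"%. It continues: "With 157 participants in each treatment arm, the power to detect a severe or life-threatening adverse event" occurring in 10% or more of men "in the phytotherapy arm at the one-sided 0.05 significance level is 80"%. No test is named. The same section provides for losses: "To allow for a 10% dropout rate over the course of the study, 350 participants will be recruited", which is 175 per arm.

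Section 8.2.3, in its closing paragraph on blood counts and serum chemistry, takes each man's worst grade in each 24-week dose period. For every dose level and laboratory measure, the proportions with grade 3 or greater "will be compared between the phytotherapy and placebo arms using Fisher's exact test". It adds: "A two-sided 0.05 significance level will be used for these comparisons".

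Section 8.2.4 treats general adverse event comparisons the same way: "A two-sided statistical test with a significance level of 0.05 will be used for these analyses".

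**The concern.** The power statement and the analysis concern the same data, blood counts and serum chemistry, but they differ in sidedness. No safety comparison in sections 8.2.3 or 8.2.4 is one-sided, so the 80% matches no test the plan will run. At the same nominal 0.05, a two-sided test needs stronger evidence of harm, so its power must be lower.

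The two sections also differ in scope. Section 8.1 speaks of a severe or life-threatening event in general. Section 8.2.3 tests one laboratory measure within one dose period at a time. A reader could take the 80% as sensitivity to laboratory toxicity overall, whereas in the planned tests the 10% rate would have to occur on a single measure within a single 24-week period.

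What is at stake is how a non-significant laboratory comparison is read. Section 1.1 says the trial uses doses above the usual ones and will inform whether tolerability justifies a long-term trial. The sensitivity quoted for the laboratory tests should be that of the tests performed.

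**Working it through.** **Inputs.** From 8.1: placebo rate p1 = 0.025 (stated as an upper bound), phytotherapy rate p2 = 0.10 (stated as a lower bound), n = 157 per arm, one-sided alpha 0.05, stated power 80%, 350 recruited. From 8.2.3: Fisher's exact test, two-sided alpha 0.05. I take the severe or life-threatening events of 8.1 to be the grade 3 or greater abnormalities of 8.2.3. The documents do not spell this out, but no other laboratory comparison is specified.

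**Step 1: reproduce the stated 80%.** For two proportions with difference d = 0.075 and mean p̄ = 0.0625:

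power = Φ{ [d√n − z√(2p̄(1−p̄))] / √(p1(1−p1) + p2(1−p2)) }

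- √(2 × 0.0625 × 0.9375) = 0.3423 and √(0.024375 + 0.09) = 0.3382.
- Without continuity correction, one-sided z = 1.645: (0.075 × √157 − 1.645 × 0.3423)/0.3382 = (0.9397 − 0.5631)/0.3382 = 1.114, so power is 86.7%.
- With continuity correction, n is replaced by (n − 1/d)²/n = (157 − 13.33)²/157 = 131.5: (0.8599 − 0.5631)/0.3382 = 0.878, so power is 81.0%.
- Exact one-sided Fisher test (enumeration as in step 2): 83.5%.

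The continuity-corrected one-sided figure is close to the stated 80%. The same method needs 154 per arm for 80%. The plan's figure therefore holds on its own terms.

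**Step 2: power of the planned test.** Let X1 ~ Binomial(157, 0.025) and X2 ~ Binomial(157, 0.10). Power is the sum of P(X1 = i) × P(X2 = j) over all pairs (i, j) for which the two-sided Fisher p-value is at most 0.05. The result is **74.3%**. The continuity-corrected approximation, with z = 1.960 in step 1, is (0.8599 − 0.6709)/0.3382 = 0.559, or 71.2%. The uncorrected one is (0.9397 − 0.6709)/0.3382 = 0.795, or 78.7%.

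| Test at 0.05, 2.5% vs 10%, 157 per arm | One-sided | Two-sided |
|---|---|---|
| Fisher's exact (enumerated) | 83.5% | **74.3%** |
| Normal approximation, continuity-corrected | 81.0% | 71.2% |
| Normal approximation, uncorrected | 86.7% | 78.7% |

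**Step 3: sensitivity of the two-sided Fisher figure**, by the same enumeration.

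| n per arm | Placebo rate | Active rate | Power |
|---|---|---|---|
| 157 | 2.5% | 10% | 74.3% |
| 170 | 2.5% | 10% | 78.4% |
| 175 | 2.5% | 10% | 79.9% |
| 157 | 2.25% | 10% | 78.5% |
| 157 | 2% | 10% | 82.5% |
| 157 | 1% | 10% | 94.9% |
| 157 | 2.5% | 10.6% | 79.8% |
| 157 | 2.5% | 11% | 83.0% |

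Only the 157 is the plan's own evaluable number. The 170 is an assumed intermediate value, and 175 means that every randomized man contributes.

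**The case against.** The case for leaving the text alone has several parts.

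- **The 80% is correctly calculated.** This stands. A reader might infer an arithmetic error in 8.1, but step 1 rules that out. The defect is a mismatch between two sections.
- **74% is a worst case.** Both rates in 8.1 are bounds, and power exceeds 80% at a 2% placebo rate or an 11% active rate. This stands as a limit on size. It does not remove the point, because 8.1 attaches 80% to any placebo rate below 2.5%, and under the planned test that fails near the bound.
- **157 may be pessimistic.** Laboratory samples are taken at weeks 12, 24, 36, 48, 60 and 72 (section 4.3), and men who stop medication are encouraged to keep attending (section 5.8). A man lost late still contributes to earlier dose periods. This also stands: the shortfall against 80% runs from essentially nothing at 175 per arm to about 6 points at 157. But 157 is the number 8.1 uses, and full numbers cannot be assumed in the last, highest-dose period.
- **Intervals are planned anyway.** Section 8.2.4 gives 95% confidence intervals for differences in adverse event proportions, and section 6.1 counts abnormal laboratory findings as adverse events. This softens the consequence but does not correct the power statement.

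A reader might also infer that the trial is too small for its safety aim, or that the laboratory tests are primary because the primary objective mentions tolerability. The documents do not support either. The sample size comes from the AUA score calculation, the primary endpoint in 8.1 and 8.2.2 is change in AUA score, and laboratory impact is the third secondary objective in 2.2.

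**Conclusion.** The inconsistency is real. The plan claims 80% power for a one-sided test and then specifies a two-sided Fisher's exact test, which has about 74% power under 8.1's own inputs. At those inputs the planned test misses a fourfold excess about one time in four (25.7%), against the one in five that 8.1 implies.

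This rests on rates of exactly 2.5% and 10%, 157 evaluable men per arm, and a single laboratory measure within a single dose period. A lower placebo rate, a higher active rate or more evaluable men closes the gap. The scope difference between 8.1 and 8.2.3 is a matter of wording. No power for laboratory toxicity overall can be calculated from the documents, so it adds nothing to the 74%.

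Severity is minor to moderate: a stated power becomes slightly less favourable, and no sample size, endpoint or analysis depends on it.

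**What to change.** Replace the power statement at the end of 8.1 with one for the planned test: about 74% power (2.5% versus 10%, two-sided 0.05, Fisher's exact test, 157 per arm; about 80% with 175 per arm), for a single laboratory measure within a single dose period. Keep the two-sided test in 8.2.3.

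Making 8.2.3 one-sided toward harm would also remove the mismatch, but it would put the laboratory tests at odds with the two-sided adverse event tests in 8.2.4. Restating 8.1 is the cleaner change. It costs one sentence and a slightly lower quoted power, with no extra participants and no change to any analysis.

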#### 8.2 Statistical Analysis Plan

#### 8.2.1 Analysis Populations

The primary analysis will be performed on the modified-intent-to-treat (MITT) population. The MITT population includes all randomized participants who meet

major eligibility criteria and who receive at least one dose of study therapy. The intent-to-treat (ITT) population will also be analyzed as a confirmatory measure.

#### 8.2.2 Analyses of the Primary Study Endpoint

The primary endpoint of this study is efficacy as determined by the change in AUA symptom score at 72 weeks. A two-group t-test will be used to compare the phytotherapy arm against placebo. A one-sided significance level of 0.05 will be used.

Mixed models repeated measures analysis will be performed to compare the phytotherapy arm with placebo over time (baseline, 24 weeks, 48 weeks and 72 weeks). This technique will control for intra-patient variation. The final covariance structure to be used in these models will be selected after all of the data have been collected. A significance level of 0.05 will be assumed for these longitudinal comparisons. Regarding multiple comparisons, differences between the two treatment groups with respect to the change in the primary endpoint from baseline to 24 weeks, baseline to 48 weeks, and baseline to 72 weeks will be examined to determine if they are significantly different from zero. If these differences are significantly different from zero, comparisons between specific timepoints (48 weeks versus 24 weeks, 72 weeks versus 48 weeks, and 72 weeks versus 24 weeks) for the primary endpoint will be performed. The Hochberg step-up method will be used for each set of these multiple comparisons. (Hochberg, 1990)

An additional analysis that will be performed using the primary endpoint is a comparison between the phytotherapy and placebo arms with respect to the proportion of participants who achieve at least a 3 point difference (improvement) in the AUA symptom score. These proportions will be compared using Fisher's exact test. A one-sided significance level of 0.05 will be used for this comparison.

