#### 3.0 PATIENT SELECTION

#### 3.1 Eligibility Criteria

To be eligible for the study, potential participants must meet all of the following eligibility criteria:

- 1. Male at least 45 years of age.
- 2. Peak urinary flow rate at least 4 ml/sec with a voided volume of at least 125 ml.
- 3. AUA symptom score  $\geq 8$  and  $\leq 24$  at both screening visits.
- 4. Voluntarily signed informed consent agreement prior to the performance of any study procedures.

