#### 3.3 Randomization and Stratification

Following a successful screening period, the participant will be officially randomized to one of the two treatment groups:

- Serenoa Repens
- Placebo

This study will use a stratified randomization scheme with equal numbers of participants in each treatment group. Stratification will be by clinical center and AUA Symptom Score (8-15; 16-24). Within each stratum, the method of randomly permuted blocks will be used to ensure that an equal number of participants are assigned to each treatment group.

Clinical Centers will randomize participants to treatment groups using a centralized, data-based system. Password protection will be implemented to ensure that only certified clinical center personnel are allowed to randomize patients. At the time of randomization, each participant will be assigned a unique medication kit identification number that will be used throughout the duration of the study.

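### The primary t-test on change is valid but adjusts for neither baseline AUA score nor the randomisation strata, giving up a probably modest amount of precision at almost no saving

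*Combined protocol and SAP*

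**What the plan says.** - Endpoint (8.1): "The primary end point of the study is change in AUA symptom score from baseline to 72 weeks".
- Primary test (8.2.2): "A two-group t-test will be used to compare the phytotherapy arm against placebo", followed by "A one-sided significance level of 0.05 will be used". No covariate or stratification factor is named.
- Planning assumptions (8.1): "a difference in the change in the AUA symptom score from baseline to 72 weeks of 2 points", "a common standard deviation of the AUA symptom score of 6 points", and "a one-sided significance level of 0.05 and a statistical power of 90" per cent, using the same two-group t-test. This gives 157 per arm, 314 in all, and 350 after a 10% dropout allowance.
- Randomisation (3.3): "Stratification will be by clinical center and AUA Symptom Score (8-15; 16-24", in permuted blocks. Section 10.2 gives 11 centers.
- Baseline (3.1, 4.1.2): the AUA score must lie between 8 and 24 "at both screening visits", and the SV2.0 value is designated as baseline.
- Mixed model (8.2.2): a further longitudinal analysis with baseline as one of its time points. No center or stratum term is named, and the covariance structure is to be chosen once all data are in.

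**The concern.** The AUA score is treated as prognostic enough to stratify on and is then not adjusted for. A t-test on change is the special case of a baseline-adjusted comparison in which the slope of the week-72 score on baseline is set to 1. Scores taken 72 weeks apart, in men selected on that same score, would be expected to have a slope below 1. Change then stays correlated with baseline, and variation that the model could remove remains in the error term.

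There is a second effect. Stratified blocks reduce the true sampling variance of the arm difference, but an unadjusted t-test estimates its standard error as if there were no strata. The reported interval is then too wide for the design.

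What is at stake is the width of the primary confidence interval and some power. The validity of the primary conclusion is not at stake.

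**Working it through.** **1. The plan's own figure.** Inputs from 8.1: difference 2, SD 6, one-sided alpha 0.05, power 90%.

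n per arm = 2 × (1.645 + 1.282)² × 6² / 2² ≈ 154.1, so 155. An exact noncentral-t search also gives 155, and the plan's 157 is within two patients of that. Dropout: 314 / 0.9 = 348.9, so 349 against the stated 350. Noncentral-t power at 157 per arm is 90.4%. The plan's figure reproduces, with 6 used as the SD of the change.

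**2. Effect of adjusting for baseline.** Let b be the slope of the week-72 score on baseline and SDb the baseline SD. Change has slope (b − 1) on baseline, so

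proportional fall in residual variance = (1 − b)² × SDb² / 6².

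The documents give neither b nor SDb, so both are assumed. Eligibility limits SDb: a uniform spread over the integers 8 to 24 has SD √((17² − 1)/12) = 4.9, and no unimodal distribution on a 16-point range exceeds 16/3 = 5.33. I take SDb from 3.5 to 4.9 and b from 0.5 to 0.8, with b = 0.3 as an extreme. Power is noncentral t at 157 per arm, difference 2, one-sided 0.05.

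| SDb | b | Variance fall | Residual SD | Power |
|---|---|---|---|---|
| t-test as planned | – | – | 6.00 | 90.4% |
| 3.5 | 0.8 | 1.4% | 5.96 | 90.7% |
| 4.0 | 0.7 | 4.0% | 5.88 | 91.4% |
| 4.0 | 0.5 | 11.1% | 5.66 | 93.1% |
| 4.9 | 0.5 | 16.7% | 5.48 | 94.3% |
| 4.9 | 0.3 | 32.7% | 4.92 | 97.4% |

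Worked line: SDb 4.9, b 0.5 gives 0.25 × 24.01 / 36 = 0.167, and 6 × √(1 − 0.167) = 5.48.

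**3. Conservatism after stratification.** A simulation used 20,000 runs, about 157 per arm, baseline uniform on 8 to 24 and allocation balanced within AUA band. It compared the t-test with ANCOVA on baseline and band. Here c is the absolute correlation of baseline with change, which equals (1 − b) × SDb / 6.

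| c | Type I error, t-test / ANCOVA | Mean SE, t-test / ANCOVA | Power, t-test / ANCOVA |
|---|---|---|---|
| 0.3 | 0.047 / 0.052 | 0.677 / 0.647 | 91.2% / 92.6% |
| 0.5 | 0.035 / 0.051 | 0.677 / 0.587 | 92.5% / 95.9% |

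With SDb 4.9, c = 0.3 corresponds to b ≈ 0.63, inside the assumed range. c = 0.5 corresponds to b ≈ 0.39, below it; the range in step 2 reaches only c = 0.5 × 4.9 / 6 = 0.41. Within that range the conservatism is therefore mild. Stratification has already given the t-test part of the power gain (91.2% rather than 90.4% at c = 0.3), so the difference between the two tests in use is smaller than step 2 alone suggests. Center effects were not simulated.

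**4. The wording of the SD.** Section 8.1 describes 6 as the SD of the score. If it is the SD at each time point, with correlation r between them, the SD of change is 6√(2(1 − r)) and the ANCOVA residual SD is 6√(1 − r²). At 157 per arm, power for t-test and ANCOVA is 80.3% and 92.7% at r = 0.3, 90.5% and 96.1% at r = 0.5, and 98.5% and 99.4% at r = 0.7 (normal approximation). ANCOVA is never worse, but the size of the gain depends on the reading. A score SD of 6 at baseline would also sit above the 5.33 limit in step 2.

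**The case against.** The strongest reply is that nothing is broken. The t-test matches the sample-size method, gives the stated 90% power on the stated assumptions, and after stratified allocation errs towards too few false positives. Change already subtracts baseline, and the blocks balance the coarse part of it. All of this stands, and it makes the point one of efficiency.

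The size is also open to challenge. A reader might infer a gain worth about a quarter of the sample, from the textbook variance factor (1 + r)/2, which is 0.75 at r = 0.5. The documents do not support that. The factor assumes equal variances at the two times; with an SD of change of 6 it implies a baseline SD of 6 / √(2(1 − r)), or 6.0 at r = 0.5 and 7.75 at r = 0.7. Both exceed the 5.33 that a unimodal distribution on 8 to 24 allows. A 25% fall would need a slope below 0.4 even at SDb 4.9.

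A reader might also infer that the t-test ignores baseline altogether, or that chance imbalance biases the result. Neither follows. Baseline enters by subtraction, and the t-test's standard error already covers the remaining imbalance.

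The mixed model might recover some precision. It is not the primary test, and no strata are specified for it.

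**Conclusion.** The point holds as a low-cost improvement in precision and in consistency between design and analysis. On an SD of change of 6, a baseline SD of 3.5 to 4.9 and a slope of 0.5 to 0.8, residual variance falls by about 1% to 17% and calculated power rises from 90.4% to about 90.7% to 94.3%. It reaches about 97% only if the slope is as low as 0.3 with the widest baseline spread. If baseline and change are almost uncorrelated (c of 0.1 or less), the variance gain is 1% or less. None of these slopes or spreads is in the documents, so the direction is firm and the size is not. Any gain from adjusting for center is unquantified. The planned test is valid, and the sample size needs no change.

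**What to change.** In 8.2.2, replace the primary t-test by an ANCOVA of change in AUA score from SV2.0 to week 72 on treatment arm, with continuous SV2.0 AUA score and clinical center as covariates, at the stated one-sided 0.05 level. Specify it before unblinding.

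Name that single outcome and that single covariate. With the SV2.0 score as covariate, analysing change or the week-72 score gives the same treatment estimate. That equivalence is lost if the mean of the two screening scores is used as the covariate instead, and SV2.0 is already the defined baseline.

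Keep the t-test as a supportive analysis, leave the sample size unchanged, and add center to the mixed model. In 8.1, state whether the SD of 6 refers to the score or to the change.

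Cost: a sentence or two of text, 1 degree of freedom for baseline plus 10 for the 11 centers (11 of the 312 available with 314 participants), and no new data or visits.

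### Optional improvement: for the three linked week-to-week contrasts, a Simes-based closed test would reject everything Hochberg rejects, and sometimes more, within the same 5% familywise error

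*Combined protocol and SAP*

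**What the plan says.** Section 8.2.2 (Analyses of the Primary Study Endpoint) first sets out the primary analysis: "A two-group t-test will be used to compare the phytotherapy arm against placebo". This is a one-sided test at 0.05 on the 72-week change, separate from everything discussed below.

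The section then adds a repeated-measures model with two sets of treatment comparisons:

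- **First set.** The arm differences in change from baseline to weeks 24, 48 and 72, which "will be examined to determine if they are significantly different from zero".
- **Second set.** This is conditional: "If these differences are significantly different from zero", the plan goes on to "comparisons between specific timepoints (48 weeks versus 24 weeks, 72 weeks versus 48 weeks, and 72 weeks versus 24 weeks) for the primary endpoint".

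On error control it says "A significance level of 0.05 will be assumed for these longitudinal comparisons" and "The Hochberg step-up method will be used for each set of these multiple comparisons". It does not say whether these comparisons are one- or two-sided, or whether the gate to the second set needs any or all of the first-set differences to be significant. Section 8.2.3 repeats the scheme for each secondary measure.

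**The concern.** The second set contains every pairwise difference among three quantities, the arm differences at weeks 24, 48 and 72. Such differences cannot be true or false in any combination. Hochberg is a general procedure that takes no account of this, so part of its adjustment guards against a situation that cannot arise.

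What is at stake is power for the questions the dose escalation raises. The first set asks whether each dose period differs from placebo. Only the second set asks whether the treatment effect changes from one dose period to the next.

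**Working it through.** **Inputs from the documents (Section 8.1).** The plan assumes "a difference in the change in the AUA symptom score from baseline to 72 weeks of 2 points", SD 6, one-sided 0.05, 90% power and 157 per arm. The plan's own figure comes first:

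n = 2 × (1.645 + 1.282)² × 6² / 2² ≈ 154.2, so 155 per arm.

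The stated 157 is close to this and gives 90.5% power. For dropout, 314 / 0.90 = 348.9, so 349 against the stated 350. The plan states no power for the timepoint contrasts.

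**Assumptions not in the documents.** Two-sided 0.05; SD 6 at each visit; equal correlation rho between visits of 0.5 to 0.8; the arm differences at weeks 24 and 48; and first-set significance judged by Hochberg.

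**Step 1: the link.** Let d24, d48 and d72 be the arm differences. Then (d72 − d24) = (d72 − d48) + (d48 − d24). If any two contrasts are zero, so is the third. The number of true nulls is therefore 3, 1 or 0, never exactly 2.

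**Step 2: error control of the closed rule.** The rule declares a contrast significant if its own p ≤ 0.05 and the Simes joint test passes: p(1) ≤ 0.0167, or p(2) ≤ 0.0333, or p(3) ≤ 0.05.

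- Three true nulls: any rejection requires Simes to pass, which has probability at most 5% under the Simes inequality. Hochberg relies on the same inequality.
- One true null: rejecting it requires its own p ≤ 0.05, which has probability at most 5%.

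**Step 3: comparison with Hochberg.** Hochberg rejects all three if p(3) ≤ 0.05, otherwise the smallest two if p(2) ≤ 0.025, otherwise the smallest if p(1) ≤ 0.0167. Each condition makes Simes pass, and every contrast Hochberg rejects has p ≤ 0.05. So the closed rule rejects all of them. It rejects more when, for example, p(1) ≤ 0.0167 and p(2) lies between 0.025 and 0.05 with p(3) above 0.05: Hochberg rejects one contrast and the closed rule two.

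**Step 4: simulation.** The standard error of an arm difference is 6 × √(2/157) = 0.677. For a contrast it is 0.677 × √(2(1 − rho)): 0.677 at rho 0.5, 0.525 at 0.7 and 0.428 at 0.8. With 400,000 to 600,000 draws per scenario:

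- Familywise error with all three contrasts null: Hochberg 0.045, Simes-closed 0.047.
- Draws in which Hochberg rejected a contrast that the closed rule missed: none.

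Power with arm differences (0, 1, 2), Hochberg to Simes-closed:

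| rho | Each adjacent step, no gate | 48 v 24, gate = any | 72 v 48, gate = any |
|---|---|---|---|
| 0.5 | 24% to 30% | 19% to 23% | 22% to 27% |
| 0.7 | 42% to 47% | 31% to 35% | 35% to 40% |
| 0.8 | 61% to 65% | 45% to 47% | 49% to 51% |

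As a check on the first row, an unadjusted two-sided test of a 1-point step at rho 0.5 has power Φ(1/0.677 − 1.96) = Φ(−0.483), about 31%. That is the ceiling for either rule.

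With differences (1, 2, 3) at rho 0.5 and gate = any, 48 v 24 rises from 23% to 30%.

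If the gate means all three first-set differences, the second set is reached in about 2% of trials under (0, 1, 2) and the gain is about 0.2 points or less. Under (1, 2, 3) the gain is about 1 to 2 points.

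**Step 5: the first set.** The changes from baseline to 24, 48 and 72 weeks have no such link. Arm differences of (0, 0, 2), for instance, make exactly two nulls true. The shortcut must not be used there.

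**The case against.** The strongest case for leaving the plan alone is that nothing in it is invalid. Hochberg is a named, cited method that holds 5%. The primary conclusion comes from a separate t-test, and the sample size was set for that test alone. The second-set contrasts are follow-up tests with no power target. All of this stands, and it is why the change is optional.

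A reader might infer more than the documents support in three ways:

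- **That the ungated column above is what the plan would gain.** It is not, because the second set is run only after the first set succeeds. Under the *any* reading both the power levels and most of the gains are lower. Under the *all* reading with no effect at 24 weeks, almost nothing is left. The gate rule matters far more to power here than the choice between Hochberg and the closed test.
- **That any joint test would do at no cost.** The guarantee of rejecting at least what Hochberg rejects belongs to the Simes version. Using a 2-df treatment-by-time test as the joint test raised average power in two-sided runs, but missed at least one Hochberg rejection in up to 0.6% of draws. Sidedness is not stated for these contrasts. In a one-sided run with differences (0, 1, 2), the 2-df version lowered power for 72 v 24 from 80.8% to 75.3%, while the Simes version gave 82.5%.
- **That the quoted sentence, which covers both sets, should be replaced for both.** The link exists only in the second set.

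**Conclusion.** The point holds as a free, optional improvement and not as an error. The link between the contrasts, the error control and the dominance over Hochberg are exact, given the Simes inequality that Hochberg already needs.

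The size of the gain is not exact. With the gate read as *any* and differences (0, 1, 2), it is about 2 to 5 percentage points for a single dose step, shrinking as rho rises. With the gate read as *all*, it runs from about 0.2 points or less (no 24-week effect) to about 1 to 2 points for (1, 2, 3), a pattern whose 72-week effect exceeds the planned 2 points. These figures use the plan's SD of 6 and 157 per arm. Two-sided testing, rho, the effect patterns and the gate reading are assumptions. The primary analysis and the 157 per arm do not change.

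**What to change.** In Sections 8.2.2 and 8.2.3, for the set 48 v 24, 72 v 48 and 72 v 24 only, replace Hochberg with:

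> A contrast is declared significant if its own p-value is at most 0.05 and the Simes joint test of the three contrasts is significant at 0.05 (ordered p-values: p(1) ≤ 0.0167, or p(2) ≤ 0.0333, or p(3) ≤ 0.05).

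Keep Hochberg for the baseline-to-24, -48 and -72-week set. Name Simes outright and do not leave a choice of joint test.

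In the same edit, state whether the gate requires any or all of the first-set differences to be significant, and whether these comparisons are one- or two-sided.

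The cost is a sentence or two in each section. The Simes test uses the three p-values the mixed model already produces, so no further data, visits or participants are needed.
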